Lymphocyte subsets in peripheral blood mononuclear cells (Cohorts 1 and 2 only) ^{22,26}		X						X		
Sample for storage ^{22,27}		X						X	X	
Spot urine sample collection for:										
Exploratory PD biomarkers ²²		X						X	X	
Study Drug Administration										
Randomization		X ²⁸								
Study drug dispensation		X			X	X				
Study drug administration		QD PO from Day 1 through Week 12								
Study drug accountability				X	X	X	X	X		

Table footnotes appear on the following page.

- 1 Baseline evaluations are to be performed pre-dose, unless otherwise specified.
- 2 At the time of this amendment, subject participation in the 25 mg cohort is complete, with participation in the 50 mg cohort fully enrolled but with subject participation ongoing. The Sponsor notes that the COVID-19 pandemic may impact the conduct of the 50 and 75 mg cohorts, with challenges potentially arising from quarantines and travel limitations affecting study subjects as well as clinic and imaging facility closures. Accordingly, safety assessments scheduled for the Week 12 and 16 visits, including sample collection for clinical laboratory tests, physical examinations, and documentation of AEs, may be performed at an alternate study center or by home health care visit. Furthermore, if the subject is unable to attend the Week 12 visit at the study center, one MRI-PDFP may be performed at any time between Week 11 and 16. If this scan is performed after Week 12, the subject must continue to receive study drug until the final scan is performed; however, study drug is not to be continued for >16 weeks. The safety of subjects who continue dosing beyond 12 weeks will be assessed during this continued dosing period by planning for blood sample collection at an alternate site or home visit at Week 12 and blood sample collection and physical examination on the last day of dosing. A 4-week off treatment safety assessment is to occur after the last dose, regardless of whether a subject receives treatment for 12 or 16 weeks.
For subjects in Cohort 3, Week 16 assessments may serve as screening assessments if within the window before the Day 1 visit.

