Due to the COVID-19 pandemic, if the subject in the 50 mg and 75 mg cohorts is unable to attend the Week 12 visit, one MRI-PDFP may be performed at any time between Week 11 and 16. If this scan is performed after Week 12, the subject must continue to receive study drug until the final scan is performed. However, study drug is not to be continued for >16 weeks.

Nonclinical and clinical data obtained to date support daily dosing with TVB-2640 for 16 weeks, as follows:

- Complete safety data from 30 subjects who received TVB-2640 25 mg for 12 weeks and available safety data from 30 subjects who received TVB-2640 50 mg for 4 to 12 weeks (ongoing cohort) as reviewed by the SRC, support continued dosing beyond Week 12 and up to and including Week 16. Safety and PK data from these 2 doses demonstrate a proportional and expected plasma exposure of TVB-2640 in subjects, further providing confidence in continued dosing.

- Safety data are available from 136 patients with cancer who received either TVB-2640 alone or in combination with a taxane of whom 72 received TVB-2640 at doses of 100 to 600 mg per day, with a mean and maximum time on treatment of 62 days (9 weeks) and 324 days (46 weeks), respectively. These doses and duration used in CLIN-002 far exceed those in the current study.
- In addition to 2 previously completed 13-week GLP toxicity studies, the Sponsor is currently conducting 2 chronic toxicology studies. ([REDACTED]
[REDACTED]
[REDACTED])
 - a. The in-life portion of a 6-month chronic toxicity study in rats has been completed (SN19-1112); adverse in-life or clinical pathology toxicities were not observed in this study. Toxicokinetic results from this study were consistent with expected exposures. The AUC of TVB-2640 at the highest dose in this study [REDACTED], over 2.5-times higher than the 50 mg dose in humans.
 - b. The in-life portion for the 9-month toxicity study in dogs has been completed through Week 36 of dosing (SN19-1113), with no in-life or clinical pathology toxicities observed through that time. The AUC of TVB-2640 at the highest dose was [REDACTED], over 2.4-times higher than the 50 mg dose in humans.

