12.2. Adverse and Serious Adverse Events

12.2.1. Definition of Adverse Events

12.2.1.1. Adverse Events (AE)

An AE is any untoward medical occurrence in a patient or clinical investigation subject administered a pharmaceutical product, and which does not necessarily have to have a causal relationship with this treatment. An AE can therefore be any unfavorable and unintended sign (including abnormal laboratory findings), symptom, or disease temporally associated with the use of an investigational product, whether or not related to the investigational product.

An unexpected AE is any event for which the nature or severity is not consistent with the information in the current Investigator's Brochure.

All AEs that occur from screening (i.e., after the ICF is signed) through 28 days after the last dose of study drug, whether or not they are related to the study drug, are to be reported in the eCRF.

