3.5. Timing of Analyses

An interim analysis for SRC review will be performed after all of the subjects in the 25 mg dose level complete the 12-week treatment period. Details on data requirements and outputs required will be maintained in the SRC Plan or other related documents.

An additional SRC analysis was performed during the COVID pandemic to confirm safety prior to allowing the option for extended 50 mg cohort dosing.

The primary analysis of efficacy will be performed when all subjects in the US 50 mg cohort finish their final visit. The primary analysis will not include any data from China, due to delays and uncertainty of enrollment in the Chinese cohort.

An End of Study final analysis will be performed when the final subject completes the study and will include cumulative data from the US and China as applicable.

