8.5.1. Adverse Events

An AE is any untoward medical occurrence in a patient or clinical investigation subject administered a pharmaceutical product, and which does not necessarily have to have a causal relationship with this treatment. An AE can therefore be any unfavorable and unintended sign (including abnormal laboratory findings), symptom, or disease temporally associated with the use of an investigational product, whether or not related to the investigational product.

An unexpected AE is any event for which the nature or severity is not consistent with the information in the current Investigator's Brochure.

Any abnormal clinical or laboratory finding considered by the Investigator to be clinically significant is to be recorded in the eCRF as part of the subject's medical history if occurring prior to the start of study drug administration and as an AE if occurring after the start of study drug administration at baseline, where the finding represents a change from baseline.

A treatment emergent AE (TEAE) is defined as any AE occurring after the first dose of study treatment. All summaries of AEs will be based on TEAEs. All AEs recorded on the eCRF, whether treatment emergent or not, will be presented in the data listing. Non-TEAEs will be flagged in the listings.

Adverse Events will be coded using MedDRA version 22.0 Mar 2019 for reporting by SOC and PT. Summaries of TEAEs by SOC and PT will be presented in descending order of overall incidence. TEAEs will also be summarized by maximum intensity as classified according to the National Cancer Institute (NCI) Common Terminology Criteria for Adverse Events (CTCAE), Version 5.0. If the AE is not included in the NCI CTCAE, then the Investigator is to determine the severity of the AE according to the criteria provided in the study protocol. The causal relationship of each AE to study drug will be determined by the Investigator according to best medical judgment as definitely related, probably related, possibly related, unlikely related, or unrelated. If the relationship between the AE and study drug is determined to be "possible", "probable", or "definite", the event will be considered to be treatment-related for the safety analyses.

Any missing severity assessments will be assumed to be Grade 3 (severe) and missing relationship assessments will be assumed to be related. All AE summaries will be produced using the safety population and displayed by treatment group and overall.

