Sponsor: Sagimet Biosciences

Protocol Number: 3V2640-CLIN-005

Version and Date: Final Version 1, 02June2020

An overview of TEAEs will be produced, including counts and percentages of subjects with any incidences of: TEAEs, TEAEs related to study treatment, serious adverse events (SAEs), TEAEs leading to study drug discontinuation, SAEs, and fatal SAEs. The number of AEs will also be included on the summary.

In addition to the overview of TEAEs, the following summaries of AEs will be provided for the safety population by treatment group and overall:

- TEAEs by SOC and PT
- TEAEs related to study treatment by SOC and PT
- CTCAE Grade 3 or higher TEAEs by SOC and PT
- CTCAE Grade 3 or higher TEAEs related to study treatment by SOC and PT
- TEAEs leading to treatment discontinuation by SOC and PT

Summaries of TEAEs by SOC, PT, and maximum severity as well as TEAEs by SOC, PT, and maximum relationship to study treatment will also be prepared.

A comprehensive listing of all AEs will be provided in a by-subject data listing. AEs that began after 84 days of dosing will be identified on the listing. In addition, the following listings will be provided:

- TEAEs related to study treatment
- SAEs
- TEAEs leading to treatment discontinuation; and
- Fatal AEs.

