APPENDIX 1. COVID-19 IMPACT AND DATA HANDLING

COVID-19 impacts on 3V2640-CLIN-005 include, but are not limited to, missed visits, inability to complete certain assessments per the protocol including Week 12 MRI-PDFF data which constitutes the data for the primary efficacy endpoint. In order to collect as much efficacy data on all randomized subjects, subjects were allowed to continue on their treatment beyond Week 12 and have their end of treatment MRI-PDFF performed at any time between Week 11 and Week 16 per protocol Amendment 5. Study drug was not permitted to be continued for more than 16 weeks. The End of Study Visit was scheduled for 4 weeks after the last dose of study drug.

Given the uncertainty of the impact of extended dosing beyond Week 12 on efficacy, the primary and secondary efficacy analyses will be performed excluding subjects who entered extended dosing beyond 12 weeks. Sensitivity analyses that include these subjects will be performed to evaluate the end of treatment efficacy.

The analysis of safety will include all collected data regardless of treatment extension.

An addendum to this SAP will be developed that documents all additional data handling techniques employed to manage COVID impacted data, if needed.

Sponsor: Sagimet Biosciences

Protocol Number: 3V2640-CLIN-005

Version and Date: Final Version 1, 02June2020

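### Crude adverse-event proportions for 50 mg against 25 mg mix dose with observation time, because only the 50 mg cohort could be dosed beyond 12 weeks; the effect is probably small and needs only extra descriptive tables.

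*SAP*

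**What the plan says.** **Who could be extended.** Protocol 9.7 allows a late scan, with dosing continued until it is done, "if the subject in the 50 mg and 75 mg cohorts is unable to attend the Week 12 visit". The cap is in SAP Appendix 1: "Study drug was not permitted to be continued for more than 16 weeks". SAP 3.5 describes the option for one randomized cohort: "An additional SRC analysis was performed during the COVID pandemic to confirm safety prior to allowing the option for extended 50 mg cohort dosing". Footnote 2 to the Schedule of Events (Protocol Table 2) shows why the lower dose is unaffected: "At the time of this amendment, subject participation in the 25 mg cohort is complete". SAP 3.1 says that several subjects were extended and gives neither a number nor a duration.

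**What is counted.** Protocol 12.2.1.1 collects adverse events "through 28 days after the last dose of study drug". SAP 8.5.1 sets no upper time limit: "A treatment emergent AE (TEAE) is defined as any AE occurring after the first dose of study treatment". Appendix 1 adds: "The analysis of safety will include all collected data regardless of treatment extension". The safety endpoints in SAP 4.2 are proportions of subjects with TEAEs, Grade 3 or 4 TEAEs and SAEs, summarized descriptively by treatment group (SAP 8.5).

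**What is done about the extra time.** For adverse events there is one provision, in SAP 8.5.1: "AEs that began after 84 days of dosing will be identified on the listing". For exposure, SAP 8.2 summarizes duration as a continuous variable and in categories, the top one being 12 weeks or more, and reports cumulative dose separately for extended subjects. For efficacy, SAP 8.3.1 and Appendix 1 plan analyses both without and with the extended subjects.

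**The concern.** Safety is one of the two primary objectives (Protocol 6.1), and Protocol 9.7 says that the adverse-event profile of the doses will inform dose optimization. The natural table for that purpose sets 50 mg beside 25 mg. Some subjects in the first column may have been watched for up to four weeks longer than any on-schedule subject in the second, and they were on study drug for that time. A crude proportion can only rise with longer observation. The 50 mg column can therefore drift upward with no dose effect, and a reader of the planned adverse-event tables cannot tell how much of a difference comes from dose and how much from time.

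**Working it through.** **The plan's own safety figure.** SAP 3.3 claims at least a 95% probability of seeing one or more events with 30 subjects and a 10% rate. Check: 1 − 0.9^30 = 0.958. It reproduces and is not in dispute, but it takes no account of the length of observation.

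**Observation windows.**
- On schedule: 12 weeks of dosing + 4 = 16 weeks.
- Maximum extension: 16 weeks of dosing + 4 = 20 weeks.
- Ratios: 20/16 = 1.25 for observation; 16/12 = 1.33 for dosing.

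**Model (assumed).** The hazard is constant and equal in all arms, so there is no drug effect. Let p be the 16-week risk and f the share of the 50 mg cohort extended by the full 4 weeks. Neither is given in the documents, so both are varied. The risk in an extended subject is pE = 1 − (1 − p)^(20/16):
- p = 10%: pE = 12.3%
- p = 30%: pE = 36.0%
- p = 50%: pE = 58.0%

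**50 mg minus 25 mg** = f × (pE − p), in percentage points:

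| f | p = 10% | p = 30% | p = 50% |
|---|---|---|---|
| 10% | 0.2 | 0.6 | 0.8 |
| 25% | 0.6 | 1.5 | 2.0 |
| 50% | 1.2 | 3.0 | 4.0 |
| 100% | 2.3 | 6.0 | 8.0 |

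For a 2-week extension the exponent is 18/16. With f = 25% the gap is 0.25 × (33.1 − 30) ≈ 0.8 points at 30% risk and 0.25 × (54.1 − 50) ≈ 1.0 at 50%.

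**Sensitivity to the clock.** If events arose only on drug, the exponent would be 16/12 with p read as the 12-week risk. A 50% risk becomes 60.3%, and the gap is 2.6 points at f = 25% and 10.3 at f = 100%.

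**Against placebo.** The 50 mg cohort's placebo subjects could be extended on the same terms.
- US only: 15 of 30 pooled placebo subjects belong to that cohort, so the gap is (1 − 15/30) = half the table values. At the same time 25 mg would look better than pooled placebo by that same half.
- With China, if the same share is extended there: 24 of 39, so (1 − 24/39) = 38% of the table values.
- Against concurrent placebo only: expected gap 0.

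**Against sampling error.** The standard error of a 30 versus 30 difference is √(2p(1 − p)/30) = 11.8 points at p = 30% and 12.9 at p = 50%. One subject in 30 is 3.3 points.

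**After the change.** Under the same model, events per subject-time at risk estimate the hazard −ln(1 − p)/16 in every arm, so the gap is 0. In a common window through Day 84 the risk is 1 − (1 − p)^(12/16) in every arm (40.5% at p = 50%), and the gap is again 0.

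**The case against.** Several points on the other side stand.

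- **Unequal exposure is not hidden.** A reader who sees only the top exposure category might infer that it is. But SAP 8.2 also summarizes duration as a continuous variable, so the mean, upper quartile and maximum will show dosing beyond 12 weeks, and cumulative dose is split out for extended subjects. What is missing is an adverse-event output that uses this information.
- **The randomized contrast is sound.** A reader might infer that 50 mg against placebo is distorted by construction. Against concurrent placebo it is not, and against pooled placebo the effect is diluted. The safety sections do not say explicitly that placebo is pooled.
- **50 mg against 25 mg is a comparison of sequential cohorts**, already open to differences in calendar time, and all safety comparisons are descriptive.
- **Keeping all safety data is right.** A reader might infer that the SAP contradicts itself by setting extended subjects aside for efficacy but not for safety. The efficacy endpoint is a Week 12 measurement, which a later scan changes; discarding safety events would be a different and worse choice.
- **A Day 84 cut as the main table would do harm**, because it would remove post-dose follow-up for every subject who finished on schedule.

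The 75 mg cohort could also be extended, but the SAP addendum reports it in its own single-column outputs, so it does not enter this comparison.

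These points reduce the size and change the remedy. They do not remove the gap: the distortion has one direction, and the planned adverse-event tables cannot show its size. Appendix 1 provides for a COVID data-handling addendum if needed, but the one supplied covers only Cohort 3.

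**Conclusion.** The point holds as a modest reporting gap. For 50 mg against 25 mg, the planned crude TEAE proportions confound dose with observation time, always toward a higher figure at 50 mg. Plausible sizes run from about 0.6 points (10% extended by 4 weeks, 30% risk) to about 2 points (25% extended by 4 weeks, 50% risk). The upper bound, on the 16- to 20-week observation clock, is about 8 points if everyone extended fully at 50% risk. Apart from the extreme cases this is less than one or two subjects in 30, and it is small against a standard error of about 12 to 13 points at 30% to 50% risk.

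The figures rest on a constant hazard, no dose effect, and assumed values for the share extended and the length of extension. If events cluster early in treatment, the drift is smaller; if they arise only on drug, it is somewhat larger. The documents do not support a claim that the safety conclusions would be materially wrong.

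**What to change.** In SAP 8.5.1 and Appendix 1, keep the all-data TEAE tables as the main display and add:

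1. Exposure-adjusted incidence by arm (subjects with an event per subject-time at risk) for TEAEs, related TEAEs, Grade 3 or higher TEAEs, SAEs, and TEAEs leading to discontinuation.
2. A supportive table of TEAEs with onset in one common window from first dose in every arm, for example through Day 84. Define it by study day of onset, which SAP 7.4 already counts from the treatment start date. The listing flag is worded in terms of days of dosing and may not capture events after Day 84 in subjects who had stopped on schedule.

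Both are useful because exposure adjustment removes the gap only if the hazard is roughly constant, while the common window does not need that assumption.

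In SAP 8.2, split the exposure category of 12 weeks or more so that extended dosing is shown separately.

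The cost is SAP wording and one extra set of descriptive tables. No new data and no change of design are needed.

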1. INTRODUCTION

This document serves as an addendum to the statistical analysis plan (SAP) version 1 dated 02June2020. The SAP Addendum is focused on details pertaining to the planned analyses for the TVB-2640 75mg Open-Label Cohort 3 and should be read along with the primary study SAP that detailed the primary analyses of data from Cohort 1 and Cohort 2.

The content of this SAP Addendum is based on the protocol version 7.0 dated 17Mar2021.

SAP Revision Chronology:

Final Version 1	02June2020	Original
Addendum 1	14Mar2022	Addendum to Original SAP

2. DESCRIPTION OF ANALYSES FOR COHORT 3

Data collected for the thirteen subjects in safety Cohort 3 will be summarized similarly to data collected for the first two study cohorts. Data collected via the EDC (CRF data) and from external vendors (laboratory data and MRI-PDFF) will be summarized, graphically presented, and listed. All summaries will be based on descriptive statistics. Continuous data will be summarized using descriptive statistics including number of subjects (n), mean, median, standard deviation (SD), first quartile (Q1), third quartile (Q3), minimum (min) value, and maximum (max) value.

Categorical data will be summarized using counts and percentage based on the number of non-missing values. For selected summaries, the number of missing values will be presented as a separate category with no percentage, if one or more subjects have missing data. Counts of zero will be presented without percentages.

Statistical significance will not be assessed for this study cohort. If any p-values are generated, they will be evaluated in order to assess study trends and not to assess statistical significance.

Statistical outputs will follow the design of those prepared for prior analyses but will include only a single column for the Cohort 3 (75mg) dose group.

Details on the analysis results and any changes from the protocol and/or prior SAP will be described in the clinical study report (CSR).

Sponsor: Sagimet Biosciences

Protocol Number: 3V2640-CLIN-005

Version and Date: Final Addendum 1, 14Mar2022

APPENDIX 2. PLANNED TABLES, LISTINGS, AND FIGURES

Sponsor: Sagimet Biosciences

Protocol Number: 3V2640-CLIN-005

Version and Date: Final Addendum 1, 14Mar2022

Type	Number	Title	Population
Table	14.1.1	Summary of Subject Disposition	All Subjects
Table	14.1.2.1	Summary of Subject Demographics	Modified Intent-to-Treat Population
Table	14.1.2.2	Summary of Subject Demographics	Safety Population
Table	14.1.3.1	Summary of Subject Baseline Characteristics	Modified Intent-to-Treat Population
Table	14.1.3.3	Summary of Subject Baseline Characteristics	Safety Population
Table	14.1.4.1	Summary of NASH History	Modified Intent-to-Treat Population
Table	14.1.4.3	Summary of NASH History	Safety Population
Table	14.1.5	Summary of Protocol Deviations	Intent-to-Treat Population
Table	14.1.6	Summary of Concomitant Medications	Safety Population
Table	14.1.7	Summary of Study Drug Exposure and Compliance	Safety Population
Table	14.2.1.1.1	Summary of Liver Fat (%) Based on MRI-PDFF	Modified Intent-to-Treat Population
Table	14.2.1.7	Summary of Liver Fat (%) Based on MRI-PDFF Log Ratio Versus Baseline	Modified Intent-to-Treat Population
Table	14.2.2.1.1	Summary of Liver Fat (%) Based on MRI-PDFF - Responder Analysis	Modified Intent-to-Treat Population
Table	14.2.3.1.1	Summary of Liver Aminotransferase Results and Change from Baseline	As-Treated Population
Table	14.2.3.4	Summary of Percentage of ALT and AST Normalization by Visit: Missing Data Excluded	As-Treated Population
Table	14.2.4.1.1	Summary of Lipid and Lipoprotein Results and Change from Baseline	As-Treated Population
Table	14.2.7	Summary of Liver Fibrosis Results as Determined by VCTE	As-Treated Population
Table	14.2.8.1.1	Summary of Metabolic Parameter Results and Change from Baseline	As-Treated Population
Table	14.2.9	Summary of Anthropometric Body Measurement Parameter Results and Change from Baseline	As-Treated Population
Table	14.3.1	Overall Summary of Adverse Events	Safety Population
Table	14.3.2	Summary of Treatment Emergent Adverse Events by SOC and PT	Safety Population
Table	14.3.3	Summary of Treatment Related Treatment Emergent Adverse Events by SOC and PT	Safety Population
Table	14.3.5	Summary of Treatment Emergent Adverse Events Leading to Treatment Discontinuation of Study Treatment by SOC and PT	Safety Population
Table	14.3.7	Summary of Treatment Emergent Adverse Events by SOC, PT, and CTCAE Grade	Safety Population
Table	14.3.8	Summary of Treatment Related Treatment Emergent Adverse Events by SOC, PT, and CTCAE Grade	Safety Population
Table	14.3.9	Summary of Treatment Emergent Adverse Events by SOC, PT, and Relationship to Treatment	Safety Population
Table	14.3.10	Summary of Selected Clinical Laboratory Results and Changes from Baseline	Safety Population
Table	14.3.14	Summary of Clinical Chemistry Shifts from Baseline	Safety Population
Table	14.3.18	Summary of Vital Signs Results and Changes from Baseline	Safety Population

Sponsor: Sagimet Biosciences

Protocol Number: 3V2640-CLIN-005

Version and Date: Final Addendum 1, 14Mar2022

Type	Number	Title	Population
Table	14.3.19	Summary of ECG Results and Changes from Baseline	Safety Population
Table	14.3.20	Summary of Clinically Significant Ophthalmologic Examination Abnormalities	Safety Population
Listing	16.2.1.1	Patient Disposition	All Subjects
Listing	16.2.1.2	Informed Consent and Randomization	All Subjects
Listing	16.2.2	Protocol Deviations	All Subjects
Listing	16.2.4.1	Demographics	All Subjects
Listing	16.2.4.2	Social History	All Subjects
Listing	16.2.4.3	Baseline Internal Laboratory Results	All Subjects
Listing	16.2.4.4	Medical History	All Subjects
Listing	16.2.4.5	NASH Confirmation Results	All Subjects
Listing	16.2.4.6	Physical Examination Results	All Subjects
Listing	16.2.4.7	Prior and Concomitant Medications	All Subjects
Listing	16.2.5.1	Study Drug Accountability	All Subjects
Listing	16.2.5.2	Study Drug Administration	All Subjects
Listing	16.2.5.3	Study Drug Dosing Adjustments	All Subjects
Listing	16.2.6.1	MRI-PDFF Results	All Subjects
Listing	16.2.6.2	Lipid and Lipoprotein Parameter Results	All Subjects
Listing	16.2.7.1	All Adverse Events	All Subjects
Listing	16.2.7.2	Treatment Related Treatment Emergent Adverse Events	All Subjects
Listing	16.2.7.3	Serious Adverse Events	All Subjects
Listing	16.2.7.4	Treatment Emergent Adverse Events Leading to Treatment Discontinuation	All Subjects
Listing	16.2.7.5	Treatment Emergent Adverse Events of Special Interest	All Subjects
Listing	16.2.7.6	Fatal Adverse Events	All Subjects
Listing	16.2.8	Selected Laboratory Results	All Subjects
Listing	16.2.8.1	Clinical Chemistry Results	All Subjects
Listing	16.2.8.2	Hematology Results	All Subjects
Listing	16.2.8.3	Coagulation and Urinalysis Results	All Subjects
Listing	16.2.8.4	Other Laboratory Results	All Subjects
Listing	16.2.8.5	Vital Signs	All Subjects
Listing	16.2.8.6	ECG Results	All Subjects
Listing	16.2.8.7	Ophthalmologic Examination Results	All Subjects
Listing	16.2.8.8	Anthropometric Body Measurements	All Subjects
Listing	16.2.8.9	FibroScan Results	All Subjects
-	-	-	-
Figure	14.2.1.2.1	Mean (SE) Percent Change from Baseline in Liver Fat (%) Based on MRI-PDFF	Modified Intent-to-Treat Population

Sponsor: Sagimet Biosciences

Protocol Number: 3V2640-CLIN-005

Version and Date: Final Addendum 1, 14Mar2022

Type	Number	Title	Population
Figure	14.2.1.3	Mean (SE) Change from Baseline in Liver Fat (%) Based on MRI-PDFF	Modified Intent-to-Treat Population
Figure	14.2.2.5	Plot of MRI-PDFF Responder Percentage Week 12 LOCF	Modified Intent-to-Treat Population
Figure	14.2.3.2.1	Mean (SE) ALT Over Time	As-Treated Population
Figure	14.2.3.2.2	Mean (SE) ALT Over Time	As-Treated Population with Baseline, Week 12 and Week 16 Data
Figure	14.2.3.5	Percentage of Subjects with ALT Normalization Over Time	As-Treated Population with Baseline ALT>ULN
Figure	14.2.3.3	Mean (SE) AST (U/L) Over Time	As-Treated Population
Figure	14.2.3.6	Percentage of Subjects with AST Normalization Over Time	As-Treated Population with Baseline AST>ULN
Figure	14.2.4.2	Mean (SE) Triglycerides (mg/dL) Over Time	As-Treated Population
Figure	14.2.4.3	Box and Whisker Plot of Triglycerides (mg/dL) Over Time	As-Treated Population
Figure	14.2.4.4	Scatter Plot of End of Treatment Triglyceride (mg/dL) Changes versus Liver Fat Absolute Changes (%)	As-Treated Population
Figure	14.2.4.5	Scatter Plot of End of Treatment Triglyceride (mg/dL) Changes versus Liver Fat Absolute Changes (%)	As-Treated Population with At Least a 30% Reduction in Liver Fat at End of Treatment
Figure	14.2.4.6.1	Scatter Plot of End of Treatment ALT Changes (%) versus Liver Fat Absolute Changes (%)	As-Treated Population
Figure	14.2.4.6.2	Scatter Plot of End of Treatment ALT Changes (%) versus Liver Fat Percentage Changes	As-Treated Population
Figure	14.2.4.7	Scatter Plot of End of Treatment ALT Changes (%) versus Liver Fat Changes (%)	As-Treated Population with At Least a 30% Reduction in Liver Fat at End of Treatment
Figure	14.2.4.8	Scatter Plot of End of Treatment Weight (kg) Changes versus Liver Fat Changes (%)	As-Treated Population
Figure	14.2.4.9	Scatter Plot of End of Treatment Weight (kg) Changes versus Liver Fat Changes (%)	As-Treated Population with At Least a 30% Reduction in Liver Fat at End of Treatment

Output numbers and titles may vary slightly in the final outputs. Any significant changes from the main study SAP to the Cohort 3 analyses will be described in the CSR.
